Aim 3: Determine how WP tobacco content impacts puffing behaviors, CO biomarker, pulmonary function, nicotine uptake, and perceived sensory attributes and appeal of WP smoking. Experienced WP smokers will participate in four laboratory sessions to smoke the research-grade waterpipe(s) *ad libitum* using the four different WP tobacco preparations characterized under Aim 1. Hypotheses: Participants will inhale a greater total puff volume and report greater appeal when smoking tobacco with medium glycerol and high sugars; nicotine uptake will not differ across the four tobaccos. Participants will report lower risk perceptions and greater satisfaction when smoking tobacco with medium glycerol and high sugars.

Aim 4: Determine the HPHC exposure ranges from the average puffing behaviors measured under Aim 2 for each tobacco. Topography data collected for all participants for each tobacco type will be averaged to produce four human-derived puffing regimens. Machine smoking will be conducted for each tobacco type, using the associated human-derived puffing regimens, to determine the range of HPHCs in the mainstream smoke. Hypothesis: Toxicant yields will be highest in the mainstream smoke generated from the medium glycerol and high sugars tobacco.

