After a successful blood sample collection, all participants will provide responses electronically to a series of questionnaires gathering information on nicotine dependence, and other subjective ratings. Participants will complete a practice session to learn how to record flavor perceptions. Height and weight will be measured for each participant.

Smoking will take place in a negative pressure room with a stable ventilation rate sufficient to keep ambient CO levels  $< 30$  ppmv. Participants will be seated in comfortable chairs designed for ease of blood collection by venipuncture. Using warm bottled water (body temperature), participants will clean their mouth and spit into a cup three times. Then, for 20 seconds, they will smell the unburned tobacco that they are assigned to smoke during that visit, and complete the questionnaire on their flavor perceptions. Participant lung function data will be collect using a handheld spirometry device. Exhaled breath CO levels will be collected for each participant just prior to the smoking session.

Participants will be encouraged to go to the bathroom prior to the start of the smoking session. The participant will be provided with a research-grade waterpipe that has been prepared with 15 g of one of the four tobacco preparations and one lit, quick-light charcoal. The participants will be instructed to smoke as they normally would or at a rate that is natural for them, through the hose/mouthpiece for up to 60 minutes. Puff topography parameters, including puff volume, duration, average and peak flow rate, and interpuff interval, will be measured continuously during the smoking session using the research-grade waterpipe. After the first 10 minutes of

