smoking, and at the end of each smoking session, participants will be asked to rate the perceived intensities of relevant sensory attributes, including “sweetness,” “harshness,” “bitterness,” “smoothness,” and overall intensity, using the general version of the Labeled Magnitude Scale (gLMS). We will also collect data on liking/disliking by using the Labeled Hedonic Scale (LHS). If participants choose to smoke for 45 minutes, they will be asked to provide exhaled breath CO levels. If any participants breath CO levels exceed 50 ppmv, the smoking session will be stopped. Otherwise, participants may smoke *ad libitum* for as long as they choose, up to 60 total minutes. At the end of the smoking session, a second exhaled breath sample will be collected, and participants will then provide answers to questions regarding flavor perception. They will give a second blood sample and perform another lung function test, as before. Afterwards they will answer questions regarding nicotine dependence and their waterpipe smoking experience.

At the end of each smoking session, participants will respond to all subjective questionnaires including the gLMS and LHS. For each test tobacco, participants will be asked to rate perceived intensities of all relevant flavor qualities (i.e., sweetness, harshness, bitterness, smoothness, overall intensity, and specific flavor) as well as their liking/disliking on gLMS and LHS.

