**Sensory Intensity and Hedonic Scales.** To determine the relative intensity including sweetness, harshness, and bitterness, and specific attributes of added flavors (e.g., apple) as well as the degree of liking/disliking for the four tobacco preparations, a psychophysical measurement technique will be employed to quantify the relationship between the tobacco flavors and their perceived intensity. Specifically, we will use the general version of the Labeled Magnitude Scale (gLMS), to obtain data that would permit ratio comparisons of perceived sensation magnitudes. The gLMS is a category-ratio scale bounded by “no sensation” at the bottom and “strongest imaginable sensation of any kind” at the top, with its intermediate intensity labels (weak, moderate, strong, and very strong) spaced logarithmically according to the empirically determined semantic magnitude. To assess the degree of liking or disliking of flavors, we will use the Labeled Hedonic Scale (LHS) to collect ratio-level data on the magnitude of liking and disliking of sensation. The properties of LHS are similar to the properties of the gLMS where the bipolar gLMS has “neutral” at its midpoint with negative descriptors to the left bounded by “strongest imaginable displeasure of any kind,” and positive descriptors to the right bounded by “strongest imaginable pleasure of any kind.”

**Biological Sample Collection.** Exhaled breath CO (via handheld electrochemical cell) and whole blood will be collected before and immediately after the WP smoking sessions according to previously developed protocols. Exhaled CO will also be measured after 45 minutes of *ad libitum* smoking, should participants choose to smoke that long. If after smoking for 45 minutes, any participant’s exhaled breath is greater than 50 ppm, the smoking session will be stopped. Within one hour of collection, the blood will be separated using centrifugation (1200 xg for 15 minutes), and the plasma layer will be transferred into a cryotube and stored at -80 °C until analysis for nicotine according to validated methods using LC-MS/MS.

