## VII. Data Analysis

### VII.1 Analysis Plan

The main research questions from the four Aims in the proposed study have the same structure for data analysis. That is, there are differences attributable to the four tobaccos in the means of the outcome measures of interest. All relevant outcome variables will be first examined with exploratory/descriptive statistical analyses that focus on describing and understanding patterns and distributions for all relevant measures (e.g., tobacco chemical content, mainstream smoke constituents, spirometry measures, topography measures, psychophysical ratings) by the four tobaccos. We will identify any potential outliers, assess distributional assumptions, and apply appropriate transformations to the outcome variables (e.g., log-transformation) if the normality assumption is violated.

For each of the four aims, the following pairwise comparisons will be performed:

$$H0i j: \mu_i = \mu_j \text{ vs. } H1i j: \mu_i \neq \mu_j$$

where  $\mu_i$  = mean target outcome for tobacco type i, and  $\mu_j$  = mean target outcome for tobacco type j. In Aims 1, 2, and 4, the data will be analyzed using one-way ANOVA models for independent outcome data and Tukey's method will be used to control type-I error rate across the six multiple comparisons. A different analysis strategy will be used in Aim 3 due to the clustered study design: participants will complete four different smoking sessions. Thus, in order to account for the hierarchical design, the data in Aim 3 will be analyzed using linear mixed models containing random subject effects. Since linear mixed models allow for incomplete data (e.g.,

due to dropout), data from all completed smoking sessions will be used in the analysis. As in the other aims, Tukey's method will be used to adjust for multiple comparisons of the tobacco treatments in Aim 3. In addition, for Aim 3, we will use linear mixed models to examine the relationships between the perceived sensory intensity ratings and the liking/disliking ratings for a given tobacco preparation.

Integrating results from Aims 1, 2 and 4 with Aim 3 of the study, the absence or presence, or exposure level of certain HPHCs and other chemical compounds across the different tobacco preparations will be mapped with the data on perceived sensory intensity such as sweetness and liking/disliking ratings.

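### Does the lack of an analysis rule for sessions stopped at the 45-minute CO check distort the total puff volume comparison?

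*Combined protocol and SAP*

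**What the plan says.** Section IV (Detailed Study Procedures for the Human Study) lets participants smoke one bowl for at most an hour: "Otherwise, participants may smoke *ad libitum* for as long as they choose, up to 60 total minutes". Those still smoking at 45 minutes give a breath sample, and "If any participants breath CO levels exceed 50 ppmv, the smoking session will be stopped". The Biological Sample Collection paragraph repeats the rule: "exhaled breath is greater than 50 ppm, the smoking session will be stopped". Puff topography "will be measured continuously during the smoking session".

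Section I gives the first Aim 3 hypothesis: "Participants will inhale a greater total puff volume and report greater appeal when smoking tobacco with medium glycerol and high sugars". For Aim 4 it adds: "Topography data collected for all participants for each tobacco type will be averaged to produce four human-derived puffing regimens".

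Section VII.1 analyses Aim 3 with "linear mixed models containing random subject effects" and, in a sentence about dropout, states that "data from all completed smoking sessions will be used in the analysis". It does not mention CO-stopped sessions, session length or censoring.

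**The concern.** A mixed model copes with absent sessions, but a shortened total is an observed value and the model takes it at face value. A stop at 45 minutes can remove up to 15 of 60 minutes. If CO rises with inhaled volume, stops should fall more often on the tobacco that is smoked harder. Its mean total would then be cut more than the others, and the difference the study hopes to show would shrink.

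The outcome matters. Total puff volume leads the Aim 3 hypotheses, Section III.C3 lists puffing topography among the primary outcomes, and Section VII.2 sizes Aim 3 on topography. The same data feed the Aim 4 machine regimens. Because a completed session is undefined, two analysts could also build different datasets.

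**Working it through.** **The plan's own power figure.** Table VII.5 gives 0.918 for r = 0.7, ρ = 0.1, d = 0.5. With N = 50, 24 degrees of freedom and two-sided α = 0.0083, the noncentrality is d / √(2(1−r)(1+ρ)/N) = 0.5 / √(2 × 0.3 × 1.1 / 50) = 4.35, and the noncentral t gives 0.918. The table reproduces.

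**Inputs the documents do not give.** The share of sessions reaching 45 minutes, the stop rate by tobacco, the link between CO and volume, and the session length a stopped smoker would have chosen. Everything below rests on assumed values.

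**Direction, in closed form.** Let mean volumes without stops be m1 > m0 and stop rates p1 and p0. Let a stop remove 15/60 = 25% of the volume, the maximum under even puffing, and be unrelated to volume within a tobacco. The observed contrast is

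m1(1 − 0.25·p1) − m0(1 − 0.25·p0),

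which is smaller than m1 − m0 only if p1·m1 > p0·m0. With m1 = 1.2 and m0 = 1 (true contrast 0.2):

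| p0 | p1 | Observed contrast | Share of true contrast |
|---|---|---|---|
| 10% | 20% | 1.2 × 0.95 − 0.975 = 0.165 | 82% |
| 10% | 10% | 1.2 × 0.975 − 0.975 = 0.195 | 97% |
| 20% | 10% | 1.2 × 0.975 − 0.95 = 0.220 | 110% |

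On the log scale, which Section VII.1 allows, equal stop rates leave the contrast unchanged.

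**Size when stops follow volume.** A simulation took puffing rate as 1 + 0.4z, a shift of 0.5 SD for one tobacco, within-subject correlation 0.6 and CO-volume correlation 0.6, with 2-30% of reference sessions that reach 45 minutes being stopped. Attenuation of the mean difference in total volume:

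| Sessions reaching 45 min | All of these intend 60 min | Intended length uniform over 45-60 min |
|---|---|---|
| 50% | 3-16% | 1.6-9.0% |
| 80% | 4-23% | 2.3-12.6% |
| 100% | 5-26% | 2.6-14.6% |

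With CO-volume correlations from 0.3 to 0.8, the middle column widens to 1-32%.

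**Power.** In the same simulation (N = 50, α = 0.0083, all intending 60 minutes), power falls from 0.90 to 0.71 if every session reaches 45 minutes and 30% of reference sessions are stopped, a loss of 0.19. If half reach 45 minutes, power is 0.35 without stops and 0.32-0.35 with them. These no-stop values fall below the planned power because the simulation puts d on puffing rate and then adds variation in session length.

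**When the tobaccos differ in CO for the same puffing.** The four products are made to differ, so this is plausible. In the same model with 80% reaching 45 minutes and 10-30% reference stops, a CO level 0.5 SD lower on the more heavily puffed tobacco inflates the contrast by about 3-4%. At 0.8 SD lower the inflation is 8-16%. With equal puffing, all sessions reaching 45 minutes and a CO shift of 0.3-0.8 SD, stops alone move the mean totals apart by about 2-8%.

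**Which sessions the text keeps.** The Section VII.1 sentence concerns dropout, and Section IV collects end-of-session measures from everyone, with no exception for a stop. Keeping stopped sessions is therefore the natural reading. Excluding them would not help: where stops follow volume, a run with a between-subject CV of 0.4 left 73-88% of the contrast after exclusion, about the same loss as keeping them.

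**The case for a change.** The strongest case for a change is that the plan is silent on a known form of truncation in its lead behavioural outcome. The direction depends on stop rates that nobody has predicted, and one sentence would settle it at almost no cost. Puffs are recorded continuously, so volume over minutes 0-45 could be pre-specified as a measure that the stop cannot touch.

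Part of this stands. The silence is real, and a reader would want the number of stops by tobacco. But stating that total puff volume means volume under the protocol as run would leave the hypothesised analysis and its result as they are. Volume to 45 minutes answers a different question, because it ignores any effect of the tobacco on later smoking. Every total is already bounded by the protocol: one 15 g bowl, one charcoal and 60 minutes. The CO stop is one more such bound.

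The Aim 4 argument is weaker. Section IV lists puff volume, duration, flow rates and interpuff interval. A stop mainly alters session length and puff count, and the protocol does not say how these enter the regimens. If the mean total did feed Aim 4, it would be 1-12% low for the more heavily puffed tobacco and 0.5-10% low for the others under the first simulation's assumptions.

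**Conclusion.** No change to the plan is needed. The missing definition is a gap in detail with a sensible default: keep the CO-stopped sessions and read total puff volume as the volume smoked under the protocol, including its CO stop. For that target the observed totals are correct and the contrast is not biased.

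Against the other target, volume without the stop, the effect could be attenuation of about 1-32%, roughly half the central values if intended lengths are spread over 45-60 minutes, or inflation of 3-16%. Stops could also create a small difference when puffing is equal. All of these rest on assumed stop rates, session lengths and CO-volume links, and no figure in the documents shows that following Section VII.1 as written would lead to a wrong conclusion. Stops can be counted by tobacco, and volume to 45 minutes derived, from records the protocol already collects. The CO rule itself is not in question.

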## VII.2. Sample Size Justification.

Since Aims 1, 2, and 4 do not involve human subjects, we expect low variability across replicates. Thus, assuming a somewhat conservative coefficient of variation (CV) of 20% and log-normal outcomes, a total of **4 replicates per tobacco preparation** will provide 80% power to detect a two-fold change in the geometric means of two groups at a conservative two-sided Bonferroni-corrected type-I error rate of 0.0083.

Our sample size for Aim 3 was selected to ensure that we have adequate power to detect moderate effect sizes in our comparisons of topography outcomes. We made the following assumptions for the power analysis:

- Based on the intravariability data analysis for the RWP, correlation coefficients within subjects ( $r$ ) were assumed to be 0.6, 0.7 or 0.8.
- Small, medium, and large effect sizes ( $d$ ) of 0.2, 0.5, and 0.8 standard deviations.
- A two-sided, Bonferroni corrected type-I error rate of 0.0083.

Our power analysis, summarized in Table VII-5, revealed that a sample size of 43 subjects will provide over 80% power to detect a moderate effect size unless the within pair correlation is high (0.2 or 0.3) and the within participant correlation is modest (0.6). However, since this power analysis assumes complete follow-up, we will recruit **60 participants** to account for a possible attrition rate of 20%, and ensure the Latin square ordering is balanced across the four tobacco types.

Table VII.5. Estimated % power to for pairwise comparisons of tobacco preparations based N = 25 pairs (50 subjects).

$r$	$\rho$	Power		
		$d=0.2$	$d=0.5$	$d=0.8$
0.6	0.1	0.108	0.803	0.998
	0.2	0.097	0.759	0.996
	0.3	0.088	0.717	0.994
0.7	0.1	0.153	0.918	> 0.999
	0.2	0.138	0.889	> 0.999
	0.3	0.125	0.857	0.999
0.8	0.1	0.255	0.989	>0.999
	0.2	0.228	0.981	>0.999
	0.3	0.207	0.971	>0.999

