### III.B3. Aim 3 Sample

We will recruit a total of 60 healthy adult men and women with the goal of having complete data sets for 50 participants. Participants will meet the eligibility criteria shown in Table III.4. Established waterpipe smokers will be recruited from advertisements

*Table III.4. Participant inclusion and exclusion criteria.*

Inclusion	Justification for Inclusion
Sufficient understanding of consent form and study procedures	Necessary to ensure that participants are adequately informed about the study
Age 21-50 years old	Legally of age to purchase, use, and possess tobacco and provide informed consent
Experienced WP smokers defined as having smoked a WP at least 3 times per month in the last month	To assure that participants are experienced WP smokers, and increase the probability of subjects being able to comfortably smoke
Willing/able to abstain from nicotine product use for at least 12 hours prior to the laboratory visits	Necessary to normalize participants' willingness to smoke WP across visits
Willing to attend four laboratory sessions at the same time of day lasting approximately 3 h each	Necessary to complete all testing sessions and provide adequate power for data analysis
Read and speak English.	To ensure that participants are adequately informed about the study and can follow the
Exclusion	Justification for Exclusion
Evident intoxication on any visit	Intoxication would interfere with informed consent and study procedures
Exhaled breath CO > 10 ppm	Indicates recent combustible tobacco use.
Pregnancy (known or suspected), trying to become pregnant, breastfeeding, unwillingness to use contraception for the duration of the study.	Unethical to enroll pregnant or breastfeeding women for smoking research
Significant smoking-related disease (by history)	Unethical to enroll subjects with tobacco-related diseases

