## IV. Detailed Study Procedures for the Human Study (Aim 3)

Study subjects will participate in a series of 4 laboratory sessions, each visit separated by at least a week, in which they smoke one of 4 tobacco preparations (blinded) using the RWP2, shown in Figure II.1, in a randomly assigned sequence, using the block randomization method. Smoking sessions will be carefully standardized: they will take place in a controlled setting, individual roomsdesignated for smoking research with sufficient ventilation rate at the Center for Tobacco

Research) within one hour of the same time-of-day after overnight nicotine abstinence ( $\geq 8$  hours, exhaled CO  $\leq 10$  ppm^173).

Research staff will light and add the charcoal and record tobacco and charcoal weights. The research-grade waterpipes will be prepared by the laboratory staff, and participants will smoke ad lib to satiation. Participants will be limited to one bowl (15 g) of tobacco and one quick-light charcoal (~10 g).

Prior to the start of the first laboratory visit, a research assistant will explain the study to the participant and answer any questions they may have. The participants will give an exhaled breath sample into the handheld CO monitor to determine if they are eligible to participate in the laboratory smoking session. If the participant's exhaled CO concentration is less than or equal to 10 ppm) they are deemed eligible to participate further, and will be asked to read the informed consent form. Once all participant questions have been answered, the participants will each be asked to sign their consent to participate in the study. Each female participant of child-bearing age will be asked to provide a urine sample for use in conjunction with a "dip-stick" pregnancy test to determine participation eligibility. Female participants with a negative urine pregnancy will be eligible to participate if they provide written agreement (via signing the consent form) to use reliable contraception throughout their participation in the study.

Each participant will then be asked to provide a pre-smoking blood sample by venipuncture. If the phlebotomist is unable to take a sufficient blood sample (10 mL) from the participant, the participant will be deemed ineligible to participate further in the study. Participants will then answer demographic and tobacco use questions.

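### The Aim 3 power statement is made for 43 subjects, but the table it cites was computed for 25 pairs (50 subjects), and the plan does not settle whether participants smoke in pairs

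*Combined protocol and SAP*

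**What the plan says.** Section VII.2 lists the assumptions for Aim 3: within-subject correlations r that "were assumed to be 0.6, 0.7 or 0.8", effect sizes d of 0.2, 0.5 and 0.8 SD, and a two-sided Bonferroni-corrected alpha of 0.0083. It gives Table VII.5 as the source for this claim: "a sample size of 43 subjects will provide over 80% power to detect a moderate effect size unless the within pair correlation is high". By high it means 0.2 or 0.3, and the exception is limited to r = 0.6. The table's caption says the powers are for "pairwise comparisons of tobacco preparations based N = 25 pairs (50 subjects"). The table also varies a second correlation, rho, over 0.1, 0.2 and 0.3.

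The section then recruits 60 "to account for a possible attrition rate of 20" per cent and to "ensure the Latin square ordering is balanced across the four tobacco types". Section III.B3 states: "We will recruit a total of 60 healthy adult men and women with the goal of having complete data sets for 50 participants".

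On the smoking arrangement, section IV says that "they smoke one of 4 tobacco preparations (blinded) using the RWP2", the dual-hose device, but of the sessions it also says that "they will take place in a controlled setting, individual roomsdesignated for smoking research".

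**The concern.** The sentence and the table it cites carry different sample sizes. The exception in the sentence picks out exactly the two d = 0.5 cells printed below 0.80 (0.759 and 0.717), so it describes the 50-subject table but attaches the result to 43. An odd number also cannot be split into whole pairs, although the caveat speaks of a within-pair correlation.

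A reader therefore cannot tell which N the stated power belongs to, or whether pairing is part of the design. The second question also affects the analysis. Section VII.1 explains the clustering only by the four sessions per participant and plans random subject effects only. If pipes are shared, that model omits the correlation on which the table's variance rests. If they are not, the table and the caveat describe a different design.

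**Working it through.** **Inputs (section VII.2).** d = 0.5 for the moderate effect; r = 0.6, 0.7, 0.8; rho = 0.1, 0.2, 0.3 (table and caveat only); two-sided alpha 0.0083.

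**Formula.** For a within-subject contrast with n subjects, the noncentrality is d / sqrt(2(1 − r)(1 + rho)/n). With n/2 pairs, power comes from the noncentral t distribution on n/2 − 1 df.

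**Step 1: reproduce the table.** At n = 50, df = 24, r = 0.6, rho = 0.1, the noncentrality is 0.5 / sqrt(2 × 0.4 × 1.1 / 50) = 0.5 / 0.1327 = 3.77. Power is 0.803, as printed. All 22 numeric cells match to three decimals (largest gap 0.0005), and the five cells printed as above 0.999 compute to 0.9998 or more. The caption fits the table.

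**Step 2: same method with 22 pairs (44 subjects, df = 21), d = 0.5.**

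| r | rho | Printed, 25 pairs | 22 pairs |
|---|---|---|---|
| 0.6 | 0.1 | 0.803 | **0.726** |
| 0.6 | 0.2 | 0.759 | 0.678 |
| 0.6 | 0.3 | 0.717 | 0.634 |
| 0.7 | 0.1 | 0.918 | 0.864 |
| 0.7 | 0.2 | 0.889 | 0.826 |
| 0.7 | 0.3 | 0.857 | **0.788** |
| 0.8 | 0.1 | 0.989 | 0.973 |
| 0.8 | 0.2 | 0.981 | 0.959 |
| 0.8 | 0.3 | 0.971 | 0.942 |

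Four of the nine cells miss 80%, not the two that the sentence excepts. Reaching 80% takes 25 pairs at r = 0.6, rho = 0.1 and 23 pairs at r = 0.7, rho = 0.3.

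**Step 3: where 43 could come from.** The documents do not say. Two calculations have 43 as their smallest N for 80% at d = 0.5, r = 0.6:
- Solo smokers, paired t with rho = 0 and df = n − 1: 42 gives 79.6%, 43 gives 80.9%.
- Normal approximation with rho = 0.1: 42 gives 79.2%, 43 gives 80.4%. At n = 43 this comes within 0.0013 of every numeric cell but matches only 7 of 22 to three decimals. If it were the source, the caption's N would be wrong.

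**Step 4: the planned analysis.** Section VII.1 uses Tukey's method in a mixed model. I used the critical value q(0.95; 4, df)/sqrt(2) with df = 3 × (pairs − 1), which is my assumption. Then 22 pairs give 81.1%, 76.9% and 72.8% at r = 0.6 (rho = 0.1, 0.2, 0.3), and 86.4% at r = 0.7, rho = 0.3.

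**Step 5: completers.** 60 × 0.8 = 48, against the goal of 50. With shared pipes, 24 pairs at r = 0.6, rho = 0.1 give 77.9% by the table's method and 85.2% under the Tukey model. With solo smoking (paired t), power at d = 0.5 for r = 0.6/0.7/0.8 is:
- N = 43: 80.9/92.2/99.0%
- N = 48: 86.2/95.2/99.6%
- N = 50: 87.9/96.1/99.7%

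**Step 6: solo or shared?** For solo smoking: section IV has individual rooms and a prepared pipe for each participant; the single-hose part of Appendix A has separate pipes in separate rooms; and section VII.1 mentions no pair clustering. Also, if four sequences are used, 60 individuals divide evenly (60/4 = 15) and 30 pairs do not (30/4 = 7.5). For sharing: section IV names the dual-hose device, Appendix A reminds participants of etiquette toward a smoking partner, and the table uses rho. Section II.7 allows either device.

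**The case against.** The strongest reply is that nothing in the trial turns on the 43. Recruitment is 60, the goal of 50 complete data sets equals the table's N, and even 43/0.8 = 53.75 (54) is below 60. The shortfall in two cells arises only if pipes are shared and only under the Bonferroni paired t test. Under the planned Tukey mixed model, 22 pairs give exactly the pattern the sentence describes. Some of the evidence for sharing is also weak. The remark in section V.1 about a screen that neither participant can see fits two people on separate pipes wired to one amplifier. The etiquette list may apply only if the dual-hose device is used.

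Most of this stands: it shows that the trial is not underpowered on account of this sentence. It does not rescue the sentence, which rests its claim on a table computed for a different N. The Tukey result depends on degrees of freedom that the plan does not state, and VII.2 itself assumes 0.0083. The named device, the etiquette list and rho still leave the pairing question open. The 48 against 50 point is minor, because one figure follows from a possible loss rate, the other is a goal, and the mixed model uses every completed session.

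**Conclusion.** The concern holds. The statement for 43 subjects is not supported by Table VII.5, which is a table for 50 subjects in 25 pairs. By the table's own method, 22 pairs fall to 72.6% and 78.8% in two cells that the sentence places above 80%. The mismatch and the reproduction of the table need only the plan's own figures.

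No real loss of power is shown. With solo smoking, 43 is adequate (80.9% at r = 0.6), the subject-only model fits, and only the table and the within-pair caveat are out of place. With shared pipes, the sentence fails by the table's method, while the planned Tukey model recovers both cells on the assumed degrees of freedom. This should be corrected because the stated N, the variance behind the power and the analysis model do not currently describe one design.

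**What to change.** State whether participants smoke alone or share a pipe, and reconcile section IV, section V.1 and both parts of Appendix A with that. Then give one N, with a matching sentence and table.

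**If alone**, as most of the procedures indicate: remove rho and the within-pair caveat, keep the subject-only model, and replace Table VII.5. Under the alpha of 0.0083 in VII.2 (paired t, df = N − 1):

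| N | r | d = 0.2 | d = 0.5 | d = 0.8 |
|---|---|---|---|---|
| 50 | 0.6 | 0.133 | 0.879 | >0.999 |
| 50 | 0.7 | 0.190 | 0.961 | >0.999 |
| 50 | 0.8 | 0.315 | 0.997 | >0.999 |
| 48 | 0.6 | 0.126 | 0.862 | >0.999 |
| 48 | 0.7 | 0.180 | 0.952 | >0.999 |
| 48 | 0.8 | 0.298 | 0.996 | >0.999 |

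If 43 is kept as the minimum, report 80.9/92.2/99.0% at d = 0.5. The cost is one table and a few words in VII.2 and III.B3.

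**If shared**: replace 43 by 50 in the sentence, list rho among the assumptions, report 77.9% for 48 completers at r = 0.6, rho = 0.1 by the table's method, and add a pair-by-session random effect so that the model matches the table's (1 + rho) variance. The cost is one extra random effect. Holding 50 completers at 20% loss would take 50/0.8 = 62.5, so 63 recruits (64 in whole pairs). Since the Tukey model gives 85.2% with 24 pairs in that cell, stating the 48-completer power is enough.

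Either way, use 48 or 50 consistently as the expected number of completers.

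### The four tobacco sequences are never named, balance of which tobacco precedes which is not promised, and the Aim 3 model lists no visit or previous-tobacco term

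*Combined protocol and SAP*

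**What the plan says.** Section IV (Detailed Study Procedures for the Human Study) has each participant smoke the four blinded tobaccos "in a randomly assigned sequence, using the block randomization method", with "each visit separated by at least a week". Before smelling and rating the assigned tobacco, "participants will clean their mouth and spit into a cup three times".

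Section VII.2 (Sample Size Justification) gives two reasons for recruiting 60: attrition of 20%, and to "ensure the Latin square ordering is balanced across the four tobacco types".

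Section VII.1 (Analysis Plan) analyses Aim 3 with "linear mixed models containing random subject effects", and "Tukey's method will be used to adjust for multiple comparisons of the tobacco treatments in Aim 3".

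Nowhere do the documents list the sequences, the type of Latin square or the block size. Nor do they mention carry-over, predecessor balance, or a visit, period or sequence term. Section I (Objectives) states the leading Aim 3 hypothesis: "Participants will inhale a greater total puff volume and report greater appeal when smoking tobacco with medium glycerol and high sugars".

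**The concern.** A Latin square guarantees that each tobacco appears equally often at each visit. It does not guarantee that each tobacco follows each other tobacco equally often. In a cyclic square (ABCD, BCDA, CDAB, DABC), B is preceded by A every time B is not first, so anything A leaves behind falls on B alone.

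Direct residue is unlikely here, given the gap of at least a week and the rinsing. What could persist is memory, contrast or expectation: the same people rate sweetness, harshness and liking of four products that differ by design in sweet additives, and the hypotheses concern appeal, satisfaction and puff volume. If such an effect differed between tobaccos and the order were unfavourable, part of a tobacco contrast would reflect what was smoked the session before. An unfavourable order also makes a later check for carry-over too imprecise to help, and analysis cannot repair that once the list has been used.

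**Working it through.** **Inputs from the documents.** Four tobaccos, four visits, 60 recruited, 20% attrition (60 x 0.8 = 48). For power: d = 0.5, r = 0.6, rho = 0.1 and "A two-sided, Bonferroni corrected type-I error rate of 0.0083" (z = 2.640).

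**Inputs assumed.** A first-order carry-over L from one tobacco only, 0.1 to 0.4 SD, because the documents give no value. Complete data, 15 participants per sequence.

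**Step 1. The plan's own power figure.** Power = Phi(d x sqrt(n) / sqrt(2(1-r)(1+rho)) - z). With n = 43: 0.5 x 6.557 / sqrt(0.88) = 3.495, and 3.495 - 2.640 = 0.855, giving 0.804 against the 0.803 in Table VII.5. All 27 cells match within 0.0013 at n = 43. (The caption says 50 subjects, which would give 0.871 in this cell; that is a separate point.)

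**Step 2. Which squares balance predecessors.** Four 4x4 Latin squares contain a given order. Counting who follows whom:

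| Square | Most often one tobacco precedes another, per 4 sequences | Worst unadjusted bias | Worst bias at L = 0.2 SD | Variance factor when previous tobacco is fitted |
|---|---|---|---|---|
| Cyclic | 3 | 0.75 L | 0.15 SD | 5.5 |
| Intermediate (first) | 2 | 0.50 L | 0.10 SD | 1.1 to 3.3 |
| Intermediate (second) | 2 | 0.50 L | 0.10 SD | 1.5 to 1.8 |
| Williams | 1 | 0.25 L | 0.05 SD | 1.10 |

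Only the Williams square has all 12 ordered pairs once. The set ABDC, BCAD, CDBA, DACB was checked: each tobacco is in each position once, and each ordered pair occurs once.

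**Step 3. Where the bias comes from.** With complete data a contrast is a difference of tobacco means.

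- Cyclic: the fixed successor follows the source in 3 of 4 sequences, so its mean shifts by 3/4 L against all three others. L = 0.1 to 0.4 gives 0.075 to 0.30 SD, which is 15% to 60% of the 0.5 SD moderate effect.
- Williams: each other tobacco follows the source in 1 of 4 sequences, so it shifts by 1/4 L against the source, and contrasts among those three are unaffected. This gives 0.025 to 0.10 SD, or 5% to 20% of 0.5 SD.
- If all tobaccos carry over equally, every mean shifts by 3/4 L and the contrasts are unbiased in any of these squares.

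**Step 4. Precision.** With subject, visit and tobacco effects, contrast variance is 2/60 = 0.0333 (in units of the residual variance) for every square. Fitting first-order carry-over removes the bias in both designs, at a variance of 0.0333 x 5.5 = 0.1833 (cyclic) or 0.0333 x 1.10 = 0.0367 (Williams).

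**Step 5. Power of the adjusted analysis**, same cell as Step 1:

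- n = 43, Williams: 3.495 / sqrt(1.10) = 3.332, power 0.756.
- n = 48, unadjusted: 3.693, power 0.854. Williams: 3.693 / sqrt(1.10) = 3.521, power 0.811. Cyclic: 3.693 / sqrt(5.5) = 1.575, power 0.143.
- n = 60: 0.932 unadjusted, 0.903 with Williams and the carry-over term.

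**Step 6. If block randomization instead means random orders.** Equal use of all 24 orders gives the same bias and variance factor as Williams, but 60/24 = 2.5, so equal use is impossible. Unrestricted random orders for 60 people give predecessor counts that run on average from about 10 to about 21 around the balanced value 60 x 3 / 12 = 15.

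**The case against.** Two stronger readings are tempting. A reader might infer that sections IV and VII.2 contradict each other. They need not: one can describe how participants are allocated and the other the set of orders, and Latin-square sequences allocated in blocks are a coherent scheme. A reader might also infer that the planned order fails to balance predecessors. The documents do not show that: a Williams square is a Latin square, and nothing says that the cyclic one will be used. Block randomization over all 24 orders would come close to Williams. The 5.5-fold variance and the 0.75 multiplier therefore belong to the worst candidate, not to a documented design.

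The carry-over size is also an assumption. The gap of at least a week, the blinding, the rinse, the practice session for flavor ratings and scale anchors that do not depend on the products all make a large effect less plausible. Finally, the adjustment is not free: at n = 43 it takes power below 80%.

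All of this stands, and it limits the point to an unspecified scheme. It does not remove it. An allocation list cannot be built from the text, three of the four candidate squares lack predecessor balance, and the safeguards address residue and labels more than memory of the last product. The power loss applies only to the sensitivity analysis, which at n = 48 still has 0.811 in the reference cell.

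**Conclusion.** The point holds as a gap in specification with a cheap improvement available, not as a demonstrated error. The sequences are not named, predecessor balance is not promised, and the stated model has no visit or previous-tobacco term.

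The variance factors in Step 4 depend only on the square chosen. The bias figures rest on an assumed first-order carry-over of 0.1 to 0.4 SD from one tobacco, complete data and no adjustment. The documents do not support the claim that the contrasts will be biased by any particular amount. They show only that the choice among Latin squares, which the plan leaves open, changes the worst-case bias threefold and decides whether a carry-over check is informative. A Williams square alone reduces the bias; removing it also needs the model term.

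**What to change.** In sections IV and VII.2, state one scheme: the four sequences of a Williams square, for example ABDC, BCAD, CDBA, DACB, with tobaccos assigned to letters at random. Allocate them in permuted blocks whose sizes are multiples of 4 and sum to 60 (15 blocks of 4, or 7 of 8 and 1 of 4), giving 60/4 = 15 participants per sequence.

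In section VII.1, add visit as a fixed effect in the Aim 3 model. With complete data, position balance already protects the contrasts from a visit trend, so the term mainly removes that trend from the residual; after dropout it also guards against lost balance. Add the previous tobacco as a prespecified sensitivity term.

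The cost is wording and the randomization list. Visits and participants are unchanged. The visit term takes 3 residual degrees of freedom (177 to 174 with 60 complete participants: 240 - 60 - 3, then 3 more), so the primary analysis loses no meaningful precision. The sensitivity analysis has about 10% larger contrast variance.
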